5.4.1.1 Subset Analyses

The robustness of the primary endpoint results will be explored by calculating the number and percent of patients meeting the primary efficacy endpoint overall (i.e., across all doses) within the following patient subsets:

- 1) Duration of ITP Disease: Persistent vs. Chronic
 - a. Persistent: between 3-12 months from date of ITP diagnosis
 - b. Chronic: >12 months from date of ITP diagnosis
- Type of Prior ITP Therapy (TPO-RAs/Steroids)
 - a. Patients on prior TPO-RAs but not on prior steroids
 - b. Patients on prior corticosteroids but not on prior TPO-RAs
 - c. Patients on prior TPO-RAs AND prior steroids
- 3) Patients with the following number of prior ITP therapies. The number of prior ITP therapies is based on the record identifier of ITP medications. Splenectomy will be counted as one prior ITP therapy.
 - a. 1 prior ITP therapy
 - b. 2 prior ITP therapies
 - c. 3 prior ITP therapies
 - d. 4 or more prior ITP therapies
- 4) Patients with at least 1 response to
 - a. prior TPO-RAs
 - b. prior corticosteroids
 - c. prior fostamatinib
 - d. prior rituximab
 - e. prior IVIG
 - f. Other prior immunosuppressive agents (i.e.: Dopsone, Azathioprine, Plaquenil, [hydroxychloroquine])
- 5) Patients who never responded to:
 - a. TPO-RA.
 - b. fostamatinib
 - c. rituximab
- 6) Patients on rilzabrutinib monotherapy vs. Patients on ITP concomitant therapy (excluding rescue therapies as patients who need rescue therapy are discontinued from the study; status determined based on the patients' use of concomitant ITP therapy). Patients on rilzabrutinib

monotherapy are patients who were on rilzabrutinib only during study treatment period without any concomitant ITP medications.

- 7) Patients on concomitant ITP medication:
 - a. TPO-RA alone
 - b. Corticosteroids alone
 - c. Both TPO-RA and steroids (with or without other ITP medications)
 - d. No concomitant ITP medication
- 8) Baseline Platelet Count: ≤15,000/µL vs. >15,000-30,000/µL
- 9) Patients who had 24 weeks of study drug under protocol version 8 (see section 3.4.11).
- 10) Patients who were TPO-RA naïve, i.e., never received TPO-RA medications

All ITP therapies will be reviewed and categorized into different types of ITP therapies, i.e. TPO-RA, corticosteroids, fostamatinib, etc. manually by the medical reviewer and a look-up dataset will be created for the analyses.

Subset analyses will not be repeated for the LTE period.

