4.3.5 Subgroup analyses

Analyses will be performed to assess the consistency on the primary endpoint (Section 4.3.2) across the following subgroups:

- Duration of ITP Disease: Persistent vs Chronic, where
 - Persistent: between 3-12 months from date of ITP diagnosis
 - Chronic: > 12 months from date of ITP diagnosis
- Duration of ITP: ≤ 3 years vs > 3 years
- Type of Prior ITP Therapy
 - Prior thrombopoietin receptor agonist (TPO-RA) but no prior corticosteroid (CS)
 - Prior CS but no prior TPO-RA
 - Prior TPO-RA and prior CS
 - Neither TPO-RA nor CS
- Prior TPO-RA
 - TPO-RA naïve, i.e., never received TPO-RA medications, Yes vs No
 - For non-TPO-RA naïve, responded to TPO-RA, Yes vs No

Note: "responded" means "resulted in platelet count ≥50,000/µL" per eCRF.

- Prior CS
 - Prior CS, Yes vs No
 - For those who exposed to CS, responded to CS, Yes vs No
- Prior IVIg or Anti-D immunoglobulin
 - Prior IVIg or Anti-D immunoglobulin, Yes vs No
 - For those who exposed to IVIg or Anti-D immunoglobulin, responded to either, Yes vs No
- Prior Rituximab
 - Prior Rituximab, Yes vs No
 - For those who exposed to Rituximab, responded to Rituximab, Yes vs No
- Participants on rilzabrutinib monotherapy vs. Participants on ITP concomitant therapy
- Participants on concomitant ITP medication
 - TPO-RA but no CS

Property of the Sanofi group - strictly confidential

- CS but no TPO-RA
- TPO-RA and CS
- No concomitant TPO-RA nor CS
- Participants with unique number of prior ITP medications by category: ≤ 3 vs ≥ 3 , and the unique ITP medications is identified by standardized medication name
- Baseline Platelet Count: <15,000/μL vs. ≥15,000/μL
- Splenectomy Yes vs splenectomy No
- Participants who had completed 24 weeks of treatment

95% confidence intervals will be calculated for the proportions using the Clopper-Pearson method.

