- A given medication can be classified as a prior medication and/or as a concomitant medication and/or as post-treatment medication. If it cannot be determined whether a given medication was taken prior or concomitantly or post, it will be considered as prior, concomitant, and post-treatment medication.

The prior, concomitant, and post-treatment non-ITP medications will be summarized for the ITT population, by anatomic and therapeutic level. The summaries will be sorted by decreasing frequency of anatomic category (ATC). Therapeutic classes are sorted by decreasing frequency within each anatomic class. In case of equal frequency, alphabetical order will be used. Participants will be counted once in each ATC category (anatomic or therapeutic) linked to the medication.

Prior ITP, concomitant non-rescue ITP, and concomitant rescue ITP therapies/medications will be summarized separately by the ATC level 4 chemical class and medication name.

The following prior ITP therapies will be presented:

- number of prior unique ITP therapies identified using standardized medication name
 - counting splenectomy as an ITP therapy
 - not counting splenectomy as an ITP therapy
- number of prior unique ITP therapies identified using standardized medication name and counting different corticosteroids as one therapy
 - counting splenectomy as an ITP therapy
 - not counting splenectomy as an ITP therapy
- number of prior ITP therapies, identified by eCRF entry records
- number of participants with the following ITP medications, respectively:
 - Corticosteroids
 - TPO-RA
 - IVIG

- Anti-D immunoglobulin
- Rituximab
- Fostamatinib
- Immunosuppressants and other immunomodulatory agents (including Cyclophosphamide)
- Dapsone
- Danazol
- Investigational ITP medications
- number of participants responded to prior ITP therapy including splenectomy,
 (i.e., resulted in platelet count ≥50,000/μL per eCRF) including splenectomy
- number of participants responded to 1) prior corticosteroids, 2) prior TPO-RA, 3) prior Rituximab, 4) prior IVIG or Anti-D immunoglobulin respectively.

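### The prior-therapy subgroups need tighter definitions: Part A counts medication records with no rule for repeats of one drug, and Part B's two groups overlap at exactly 3

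*SAP*

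**What the plan says.** **Part A SAP.** Section 5.1.3 (ITP History) and section 5.4.1.1 (Subset Analyses, item 3) give the same counting rule: "The number of prior ITP therapies is based on the record identifier of ITP medications". Both add that "Splenectomy will be counted as one prior ITP therapy". Item 3 then reports the primary endpoint for patients with 1, 2, 3 and "4 or more prior ITP therapies". Neither section defines the identifier or says what happens when one drug appears in several records. Section 5.4.1.1 closes with a manual medical review: "All ITP therapies will be reviewed and categorized into different types of ITP therapies". That step sorts therapies by class and is not described as merging repeats.

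**Part B SAP.** Section 4.3.5 uses a different unit and a single cut: "Participants with unique number of prior ITP medications by category: ≤ 3 vs ≥ 3", where "the unique ITP medications is identified by standardized medication name". It does not say whether splenectomy counts. Appendix 2 (section 5.2) lists several baseline counts side by side: the "number of prior unique ITP therapies identified using standardized medication name", with and without splenectomy; the same with all corticosteroids treated as one; and, as a separate line, a count taken from eCRF entry records.

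**The concern.** The number of prior therapies tells a reader how heavily pretreated the patients were, and the subset table shows whether response holds up as that number rises. A record is not necessarily a therapy. If a second or third course of the same drug gets its own record, the Part A count measures entries rather than distinct treatments. The error can run in one direction only, upward. The top category could then mix patients who had four or more different treatments with patients who repeated one or two.

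In Part B the unit is clear but the groups are not. Someone with exactly 3 unique medications meets both conditions, so the programmer must either count that person twice or decide where 3 belongs, in an open-label study whose data can be seen.

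**Working it through.** The documents state no figure to reproduce on this point. The check is whether each rule yields a well-defined, non-overlapping classification.

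**Step 1. Part A categories.** Inputs: categories 1, 2, 3 and 4 or more (Part A SAP 5.4.1.1, item 3). Each count from 1 upward falls in exactly one category. The cut-points are sound; the open question is the unit.

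**Step 2. Part A unit.** Suppose drug *k* has *r_k* records, and let *s* = 1 if the patient had a splenectomy and 0 otherwise.

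- Count by record: R + s, with R = Σ r_k
- Count by distinct drug: U + s, with U = the number of different drugs
- Excess: R − U = Σ (r_k − 1), which is never negative
- Category shift: min(R + s, 4) − min(U + s, 4)

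Hypothetical patient with three prednisone records, one IVIg record and no splenectomy: R = 3 + 1 = 4 and U = 2, so the excess is (3 − 1) + (1 − 1) = 2. The patient moves from category 2 to category 4 or more. A patient who already has four or more distinct therapies cannot change category, although the ITP-history count in 5.1.3, which is not capped, can still rise.

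This step assumes that repeat courses have separate records. Two places bear on that:

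| Place | What it shows |
|---|---|
| Part A SAP 5.1.3 and 5.4.1.1 | Counting by record identifier; identifier undefined; no merging rule |
| Part B SAP Appendix 2 | Record count and unique-name count listed as different quantities in the same study |

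The second makes the assumption plausible but does not prove it. The case report form is not among the documents, so the number of patients who would move is not computable.

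**Step 3. Part B cut.** Testing the integer counts 1 to 14 against three versions of the cut:

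| Cut | Counts in both groups | Counts in neither |
|---|---|---|
| ≤3 vs ≥3 (as printed) | 3 | none |
| ≤3 vs >3 | none | none |
| <3 vs ≥3 | none | none |

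As printed, the two denominators sum to N + n₃, where n₃ is the number with exactly 3. Planned N is about 23 (Part B SAP section 2). The documents do not give n₃, so the values below are assumed:

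| n₃ (assumed) | Sum of denominators |
|---|---|
| 0 | 23 + 0 = 23 |
| 2 | 23 + 2 = 25 |
| 5 | 23 + 5 = 28 |
| 8 | 23 + 8 = 31 |

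Either exclusive cut brings the sum back to N.

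**The case against.** **The identifier may already be one per therapy.** This stands as a real limit. A reader might infer that every repeat course or dose change adds one to the Part A count. No section says so, and dose changes in particular are nowhere described as creating new records. What can be said is that the rule as written does not exclude it.

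**Part A already gives context.** Section 5.1.3 also reports the numbers of corticosteroid, TPO-RA and other prior therapies, and section 5.1.5 tabulates prior ITP medications by preferred name. These help a reader judge whether one class drives the total. They do not correct the categories in the subset table.

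**Unique drug name is only one convention.** True: by that rule prednisone and dexamethasone are two therapies, and Part B Appendix 2 also shows a version with corticosteroids collapsed. It is nonetheless the unit the sponsor chose for the Part B subgroup.

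**The two parts are not made incomparable.** A reader might conclude that they are. If Part A does count records, the eCRF-record line in Part B Appendix 2 offers a broadly matching baseline count. The subgroups differ in cut-points in any case, and no cross-part comparison of them is planned. What remains is that the two subset tables should not be read side by side without noting the different units.

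**The Part B overlap may be a slip or a misread symbol.** Possible. The text was extracted from PDF, although exclusive cuts in the same list (ITP duration in years, baseline platelet count) came through intact. As each subgroup is a stand-alone proportion with its own interval, double counting distorts no test. The overlap still has to be resolved before the table can be programmed.

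**Conclusion.** The point holds as a matter of definition, with modest consequences. In Part A the counting rule lacks a merging step. If repeat courses are separate records, patients can be placed above the category that their distinct therapies warrant, never below it; how many is unknown. In Part B the cut as printed puts exactly 3 in both groups, provided that the symbol was extracted correctly.

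It would be wrong to infer that the efficacy results are affected. Part A SAP 3.8 plans no hypothesis testing, the subset analyses in both SAPs are descriptive, and neither the primary estimates nor the sample sizes depend on this count. It would also be wrong to say that 3 clearly belongs in the lower group. The duration split in the same list places its boundary value below, while the platelet split places its boundary value above, so the documents do not settle it.

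**What to change.** **Part A (5.1.3 and 5.4.1.1, item 3).** Define the record identifier. Base the ITP-history count and the subset on distinct therapies by WHODRUG preferred or standardized name, plus one for splenectomy, and keep the record count as a separate descriptor. The coded names already exist under sections 3.8 and 5.1.5. The medical-review look-up is not the right source, because it classifies by type and would merge different TPO-RAs. Part B SAP 1.1 says that a Part A study report has been prepared, so this would be a supplementary table, labelled as post hoc. If the identifier turns out to be one per therapy, a clarifying sentence is enough.

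**Part B (4.3.5).** Check the source PDF. Then state one exclusive cut, either ≤3 vs >3 or <3 vs ≥3, as the sponsor intended, and say whether splenectomy counts.

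**Cost.** A recount from coded data and one extra table for Part A; one line of text for Part B. No new data are needed. The downside is that Part A patients may look somewhat less heavily pretreated.

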5.4.1.2 Predictive Platelet Count Analysis

The following three (3) predictive values of platelet count will be crossed tabulated in a performance metrics with two platelet outcomes.

Predictive values of platelet count:

- i. $\geq 30,000/\mu L$ on Study Day 8
- ii. ≥ 20,000/μL above baseline on Study Day 8
- iii. $\geq 50,000/\mu$ L at any time over the first 8 weeks of study drug treatment

Platelet outcome variables:

- i. Primary efficacy response Achieved primary efficacy platelet response (see Section 5.4.1)
- ii. Durability of response Achieved 8 out of final 12 platelet counts \geq 50,000 μ/L (see Section 5.4.3.6)

The performance metrics will be constructed as follow:

	Achieved outcome _i	Did not achieved outcome _i	Total
Predictive Value _i (Y)	а	b	a + b
Predictive Value _i (N)	С	d	c + d
Total	a + c	b + d	a + b + c + d

The sensitivity, specificity, Positive Predictive Value (PPV) and Negative Predictive Value (NPV) will be calculated as:

- Sensitivity = a/(a +c)
- Specificity = d/(b+d)

- PPV = a/(a+b)
- NPV = d/(c+d)

This analysis will be performed for ITT population overall and patients started with 400 mg BID. This analysis will not be repeated for the LTE period.

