5.4.1 Primary Efficacy Endpoint

Platelet count is measured at visits as specified in the Schedule of Assessments (Table 3 to Table 6).

The primary efficacy endpoint is:

 Proportion of patients able to achieve two or more consecutive platelet counts, separated by at least 5 days, of ≥ 50,000/µL AND an increase of platelet count of ≥ 20,000/µL from baseline, by dose level, without use of rescue medication in the 4 weeks prior to the latest elevated platelet count.

The number and percentage of patients who meet the primary efficacy endpoint criteria in the main treatment period will be tabulated by dose level and overall. A 95% confidence interval will be calculated for the proportions using the Clopper-Pearson method. The response will be attributed to the dose level at the visit prior to the first of the two consecutive scheduled platelet counts occurred that are at least 5 days apart, see table below. A patient can have multiple responses within the same dose level and/or at different dose levels. This table will be repeated by starting dose.

Example 1: Patient had a response at 200 dose only			Example 2: Patient had a response at 200 and 400 doses.						
Visit	Dose	Platelets	Response	Dose that	Visit	Dose	Platelets	Response	Dose that
	dispensed			response is		dispensed			response is
	at this visit			attributed to		at this visit			attributed to
C1D1	200	25			C1D1	200	25		
C1D8	200	30		200	C1D8	200	30		200
C1D15	200	35		200	C1D15	200	35		200
C2D1	400	51	Υ	200	C2D1	400	51	Υ	200
C2D8	400	55		400	C2D8	400	55	Y	400
C2D15	400	42		400	C2D15	400	53		400
C3D1	600	39		400	C3D1	600	39		400
C3D8	600	40		600	C3D8	600	40		600
C3D15	600	41		600	C3D15	600	41		600
Example 3: Patient had a response at 200 and 600 doses.			Example 4: Patient had a response at 200, 400 and 600 doses.						
Visit	Dose	Platelets	Response	Dose that	Visit	Dose	Platelets	Response	Dose that
	dispensed			response is		dispensed			response is
	at this visit			attributed to		at this visit			attributed to
C1D1	200	25			C1D1	200	25		
C1D8	200	30		200	C1D8	200	30		200
C1D15	200	35		200	C1D15	200	35		200
C2D1	400	51	Υ	200	C2D1	400	51	Υ	200
C2D8	400	55		400	C2D8	400	55	Υ	400
C2D15	400	42		400	C2D15	400	53		400
C3D1	600	43		400	C3D1	600	39		400
C3D8	600	59	Υ	600	C3D8	600	59	Υ	600
C3D15	600	59		600	C3D15	600	59		600

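### In the Part A predictive analysis, a high count in the first 8 weeks is scored against a response that can occur in those same weeks, so the table measures concordance rather than forward prediction

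*SAP*

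**What the plan says.** SAP Part A 5.4.1.2 sets three early markers against two outcomes in a 2x2 layout. Marker iii is any count of at least 50,000/µL "at any time over the first 8 weeks of study drug treatment". Outcome i is "Achieved primary efficacy platelet response (see Section 5.4.1"). Outcome ii is durability: "Achieved 8 out of final 12 platelet counts" at or above 50,000/µL.

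Section 5.4.1 defines the primary response as "two or more consecutive platelet counts, separated by at least 5 days", each at least 50,000/µL, with a rise of at least 20,000/µL from baseline and no recent rescue. It counts the patients "who meet the primary efficacy endpoint criteria in the main treatment period will be tabulated by dose level and overall". The window is thus the whole main period, weeks 1 to 8 included.

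On the analysis set, 5.4.1.2 says: "This analysis will be performed for ITT population overall and patients started with 400 mg BID". It sets no Week 8 landmark, does not set aside patients who have already responded, and does not limit the outcome to later counts.

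**The concern.** PPV and NPV are normally read forward in time: given what is known at Week 8, what happens next? Here a patient who responds in Week 5 is counted as correctly predicted by a marker built from the same Week 5 count. Some of the apparent prediction is the outcome predicting itself.

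At stake is how the Part A table is read. Protocol 3.2.2 makes prediction from the first 8 weeks a Part B efficacy objective, and the Part B synopsis lists the same three markers. Part A figures for marker iii against outcome i could be taken as a precedent, although they answer a different question from the Part B analysis.

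**Working it through.** **Plan's own figure.** The documents state no sensitivity or PPV, so there is none to reproduce. The one borrowed planning figure is the 40% primary response rate (protocol 10.5). Its quoted half-width checks: 1.28 × √(0.4 × 0.6 / 15) = 0.162, or 16 points.

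**Direction, with no modelling assumption.** Let a, b, c, d be the SAP's cells: marker-positive with and without the outcome, then marker-negative with and without it. Let e be the patients whose only response has its first count in weeks 1 to 8. That first count is at least 50,000/µL, so all e patients are marker-positive and sit in cell a. Under a Week 8 landmark, only a response with both counts after Week 8 counts, so e moves from a to b:

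- Sensitivity: a/(a+c) becomes (a−e)/(a−e+c), never higher.
- PPV: a/(a+b) becomes (a−e)/(a+b), lower by exactly e/(a+b).
- Specificity: d/(b+d) becomes d/(b+d+e), never higher.
- NPV: d/(c+d) in both.
- Outcome prevalence falls by e/n, where n = a+b+c+d.

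A check on 100,000 random tables found no violation for sensitivity, specificity or PPV.

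**The SAP's own examples.** The four patients in 5.4.1, starting with "Example 1: Patient had a response at 200 dose only", all have 51 at C2D1 (Day 29) and 55 at C2D8 (Day 36), inside the marker window. Only Examples 3 and 4 also have a pair after Week 8 (59 and 59 at C3D8 and C3D15). PPV is 4/4 as written and 2/4 with the landmark; sensitivity is 4/4 and 2/2. These examples illustrate dose attribution and are not data.

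**Size, by simulation.** All scenarios are assumed: one count per week, no dropout, the same patients in both tables. Each cell shows as written → landmark, in percent.

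| Assumed scenario | Weeks | Sensitivity | PPV | Outcome prevalence |
|---|---|---|---|---|
| Independent counts, 10% chance each | 24 | 71 → 57 | 24 → 13 | 19 → 13 |
| Same | 12 | 88 → 57 | 15 → 3 | 9.7 → 2.8 |
| Independent counts, set to 40% response | 24 | 82.0 → 74.6 | 43.8 → 28.4 | 39.9 → 28.3 |
| Same | 12 | 96.0 → 87.9 | 43.7 → 13.5 | 40.0 → 13.4 |
| Runs: a high count is followed by another with chance 0.5 | 24 | 50.9 → 33.8 | 66.2 → 32.6 | 40.0 → 29.7 |
| Runs: chance 0.8 | 24 | 43.4 → 31.6 | 86.5 → 52.2 | 40.0 → 33.1 |
| Durable: 35% respond, 70% of counts high after onset (mean 4 weeks), 3% otherwise | 24 | 86.7 → 86.5 | 69.9 → 68.9 | 36.1 → 35.7 |
| Durable: 40% respond, same 70% and 3% | 24 | 89.7 → 89.6 | 74.7 → 73.8 | not tabulated |
| Same | 12 | falls about 1 point | 72 → 57 | PPV/prevalence 1.93 → 1.91 |

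**How much of the PPV fall is prevalence.** In the 10% case the marker-positive rate is 1 − 0.9^8 = 57%. At 24 weeks prevalence falls by about 6 points, so PPV falls by 6/0.57, about 11. As written, PPV exceeds prevalence by 24 − 19 = 5 points; after the landmark, by nothing. At 12 weeks the excess is 15 − 9.7, again about 5. The self-prediction here is worth about 5 points of PPV, not the full 11 or 12.

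**Outcome ii.** With k weeks of treatment and one count a week, the final 12 counts run from week k − 11 to week k. At k = 24 that is weeks 13 to 24, so there is no overlap. If the final 12 follow each patient's own duration, overlap lasts while k − 11 ≤ 8, that is up to 19 weeks. At k = 12 only 4 counts fall after Week 8, so 8 high counts force at least 4 in the marker window, and sensitivity and NPV are 100% by arithmetic.

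**The case against.** The best defence is that little hangs on this table. SAP Part A 3.8 plans no hypothesis testing, and no sample size or dose rule depends on these figures. The same section already pairs marker iii with a durability outcome that is separate in time for 24-week patients. Individual platelet profiles and the Kaplan-Meier analysis of time to first high count show timing directly. If responses are durable, as protocol 2.2 describes for 400 mg BID, the 24-week figures hardly move. All of this stands, and it limits the weight of the point without removing the overlap.

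A landmark also has a price. Under SAP 5.4, patients given rescue are discontinued, so a table limited to patients treated beyond Week 8 drops treatment failures selectively. That stands too, and shapes the fix.

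A reader might infer three stronger things that the documents do not support:

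- That the Part B objective is compromised. SAP Part B 4.3.1 scores its endpoint from Week 14 to Week 25, so a marker from weeks 1 to 8 cannot overlap it.
- That outcome ii has the same fault for the 12-week patients of protocol version 7.0. This depends on Section 5.4.3.6, whose text is not shown. The related 4-of-8 endpoint in 5.4.2.2 follows each patient's own duration, but it also has versions fixed to Weeks 17 to 24.
- That the 10% independent case gives the size. It implies primary response rates of only 9.7% (12 weeks) and 19.1% (24 weeks), against the planned 40%, and it allows no response to persist.

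**Conclusion.** The point holds for marker iii against outcome i. As written, sensitivity, specificity and PPV are at or above their Week 8 landmark values, and NPV is the same. That follows from the SAP's definitions alone, for a fixed set of patients.

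The size cannot be fixed from the documents. For 24-week patients, the fall in sensitivity and PPV runs from about 0 and 1 points (durable responders) to about 14 and 11 (independent counts at 10%). For 12-week patients the same two assumptions give about 1 and 14 points, and about 30 and 12. Other assumed patterns move PPV further: about 34 points at 24 weeks with transient runs, and about 30 at 12 weeks with independent counts set to a 40% response. Part of every PPV change is lower prevalence.

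Outcome ii is clear of the problem for 24-week patients and conditional for 12-week patients. The Day 8 markers share at most one count with the outcome, and no effect was computed for them. This is a minor point of labelling and interpretation in a descriptive analysis.

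**What to change.** - Keep the ITT table of marker iii against outcome i, but call it concordance. Print outcome prevalence beside PPV.
- Add a landmark table for the same pair. Count only responses with both counts after Week 8, in patients still on treatment with counts after Week 8. Report how many patients are excluded and why.
- State how the final 12 counts are chosen. If they follow each patient's own duration, also show outcome ii for patients whose final 12 counts all fall after Week 8. On that reading, this drops every 12-week patient and anyone treated for less than about 20 weeks.

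SAP Part B 1.1 says a Part A report has already been prepared, so in practice this is a supplementary table and a change of label. It needs no new data.

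The cost is selection. The landmark set loses patients who stopped early, including those discontinued for rescue, so it conditions on staying on treatment. Because the patients differ, even its NPV need not match the ITT table. It should supplement the ITT table, not replace it.
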